5.5. Dose Selection

The dose regimen of migalastat proposed for evaluation in pediatric subjects with Fabry disease (150 mg QOD) weighing \geq 45 kg (99 pounds) is the same as the adult dose and is supported by simulation results from a population pharmacokinetic model derived using data from adults, based on body weight (Migalastat Abbreviated Report of the Simulations of Migalastat in Pediatric Patients with Fabry Disease, 20 October 2016).

6. **OBJECTIVES AND PURPOSE**

6.1. **Primary Objective**

The primary objective of this study is as follows:

• to assess the long-term safety of migalastat treatment in pediatric subjects diagnosed with Fabry disease and who have variants in the gene encoding α-Gal A amenable to treatment with migalastat

6.2. Secondary Objectives

The secondary objectives of this study are as follows:

- to characterize the PD of migalastat in pediatric subjects diagnosed with Fabry disease and who have *GLA* variants amenable to treatment with migalastat
- to assess the efficacy of migalastat in pediatric subjects diagnosed with Fabry disease and who have *GLA* variants amenable to treatment with migalastat

7. INVESTIGATIONAL PLAN

7.1. Study Design

This is a long-term, open-label, uncontrolled, multicenter study to evaluate the safety, PD, and efficacy of migalastat treatment in pediatric subjects over 12 years of age with Fabry disease and with amenable *GLA* variants. Subjects will enroll in this study following completion of migalastat Study AT1001-020.

Enrollment in this study should immediately follow completion of Study AT1001-020 in order to maintain the continuity of treatment. As appropriate, assessments performed at the End of Treatment visit for Study AT1001-020 will be utilized for Visit 1 (baseline) assessments for this study.

Subsequent visits for this study will be scheduled every 6 months with interim telephone contacts at intervening 3-month intervals in order to monitor safety. In general, subjects must have completed Study AT1001-020 to be eligible for enrollment in this study. However, subjects who withdrew from the prior study for a reason not related to the safety or efficacy of migalastat may be eligible to participate in this study upon approval by the Amicus medical monitor.

Subjects will remain on the same dose of migalastat that they were receiving in Study AT1001-020. If a subject's weight decreases to below 43 kg, an unscheduled visit will be arranged 2 to 4 weeks later in order to monitor the subject's weight.

Subjects who are eligible and able to receive reimbursed product at the completion of Study AT1001-020 or during the current study will be switched to Galafold, if continued treatment with migalastat is desired. Subjects who are unable to secure reimbursed product may continue treatment in the study, or via an early access or other program. Regardless of treatment choice, subjects may also enroll in the Fabry Registry that is being conducted under a separate protocol.

7.2. Duration of Treatment

Subjects will continue on the study until the date of regulatory approval or marketing authorization for pediatric patients with Fabry disease and availability of reimbursed product in the participating subject's country, or study termination by Amicus. Since subjects will be entering this study as they complete Study AT1001-020, the duration of treatment will vary among subjects.

7.3. Details of Study Treatment

Migalastat will be supplied as 150-mg capsules. Migalastat capsules contain 123 mg migalastat free base, which is equivalent to 150 mg migalastat HCl.

7.3.1. Administration of Study Treatment

Migalastat will be administered QOD during the treatment period. Capsules are to be taken with water at the same time of day during the QOD dosing schedule.

Subjects will be instructed not to eat for at least 2 hours before and for 2 hours after administration of study drug. Water can be consumed during this period.

Study drug should not be taken on 2 consecutive days. If a dose is missed entirely for the day, the subject should take the missed dose of study drug only if it is within 12 hours of the time the dose normally is taken. If more than 12 hours have passed, the subject should resume taking study drug at the next planned dosing day and time according to the every-other-day dosing schedule.

7.3.2. Study Drug Interruptions

The investigator may choose to interrupt administration of study drug in case of an AE (eg, abnormal result of an assessment or laboratory test) or for administrative reasons.

Any interruption in dosing must be documented in the subject's electronic case report forms (eCRFs) and source medical record. The medical monitor/Clinical Project Manager should be informed as soon as possible after the decision is made to interrupt study drug for a subject.

7.3.3. Treatment Compliance

Treatment compliance will be assessed at each clinic visit through subject interview, and by comparing the amount of study drug that should have been taken since the last study visit with the amount of study drug returned. If a subject is not compliant with study drug administration, the investigator (in consultation with the medical monitor) will consider whether the noncompliance should warrant withdrawal of the subject from the study.

7.4. Concomitant Medications

Concomitant medications, including vaccinations, and any medication taken at any time throughout the study must be recorded in the eCRFs, along with the reason for use, dates of administration, dosage, frequency, and route of administration. Medication continuing from the previous study also must be recorded.

7.5. Prohibited Medications

Use of the following medications or treatments during this study is prohibited and will result in withdrawal from the study:

- investigational/experimental therapy
- gene therapy
- Enzyme replacement therapy (eg, Replagal[®] [agalsidase alfa], Fabrazyme[®] [agalsidase beta])
- Glyset[®] (miglitol)
- Zavesca[®] (miglustat)

8. SELECTION AND WITHDRAWAL OF SUBJECTS

8.1. Number of Subjects

The number of subjects to be enrolled will be dependent on the number of eligible subjects completing migalastat treatment in Study AT1001-020 and who consent to enroll in this open-label extension study.

8.2. Eligibility Criteria

Adherence to the eligibility criteria for participation in this study is essential to ensure scientific integrity, regulatory acceptability, and subject safety. Waivers of inclusion/exclusion criteria will not be granted.

8.2.1. Inclusion Criteria

Subjects must meet all of the following criteria to be considered for enrollment in the study:

- 1. Male or female subjects, diagnosed with Fabry disease > 12 years of age who completed Study AT1001-020
- 2. Subject's parent or legally authorized representative is willing and able to provide written informed consent and authorization for use and disclosure of personal health information or research-related health information, and subject provides assent, if applicable
- 3. If of reproductive potential, both male and female subjects agree to use a medically accepted method of contraception throughout the duration of the study and for up to 30 days after their last dose of migalastat

8.2.2. Exclusion Criteria

Subjects who meet any of the following criteria will be excluded from participating in the study:

- 1. Subject's last available estimated glomerular filtration rate (eGFR) in the previous study was $< 60 \text{ mL/min}/1.73 \text{ m}^2$
- 2. Subject has advanced kidney disease requiring dialysis or kidney transplantation
- 3. Subject received any investigational/experimental drug, biologic, or device within 30 days before baseline, with the exception of migalastat
- 4. Subject anticipates starting gene therapy during the study period
- 5. Subject has any intercurrent illness or condition at Visit 1 that may preclude the subject from fulfilling the protocol requirements or suggests to the investigator that the potential subject may have an unacceptable risk by participating in this study
- 6. Subject has a history of allergy or sensitivity to migalastat (including excipients) or other iminosugars (eg, miglustat, miglitol)
- 7. Subject requires treatment with Replagal (agalsidase alfa) or Fabrazyme (agalsidase beta)
- 8. Subject requires treatment with Glyset (miglitol) or Zavesca (miglustat)
- 9. Female subject is pregnant or breast-feeding, or is planning to become pregnant during the study period

10. In the opinion of the investigator, the subject and/or parent or legally-authorized representative is unlikely or unable to comply with the study requirements

8.3. Withdrawal Criteria

8.3.1. Reasons for Discontinuation/Withdrawal

Subjects may discontinue study drug, withdraw from the study, or be withdrawn from the study for any reason including, but not limited to, the following reasons:

- at their own request or at the request of their parent or legally-authorized representative
- if, in the investigator's opinion, continuation in the study would be detrimental to the subject's well-being
- occurrence of an intolerable AE as determined by the investigator, subject, and/or parent or legally-authorized representative
- failure of the subject to comply with the study visit schedule
- persistent noncompliance, at the discretion of the investigator
- pregnancy
- subject becomes eligible for reimbursed product
- inability to contact subject (ie, subject is lost to follow-up)
- Amicus medical monitor request

8.3.2. Handling of Withdrawals

The reason for and date of discontinuation or withdrawal must be recorded in the eCRF and in source documents. All subjects who discontinue study treatment will be encouraged to complete an early termination (ET) visit and follow-up safety assessments.

The investigator must make every effort to contact subjects who are lost to follow-up to schedule end-of-study assessments. Attempts to contact subjects who are lost to follow-up (eg, times and dates of attempted telephone contact, documentation of a registered letter) must be recorded in the subject's source document.

If a subject wishes to discontinue treatment, the investigator must determine the extent that a subject may be willing to continue participation in the study, as follows:

- the parent or legally-authorized representative and/or subject wants to discontinue study drug, but agrees to the follow-up procedures
- the parent or legally-authorized representative and/or subject wants to discontinue study drug and all follow-up procedures
- the parent or legally-authorized representative and/or subject wants to revoke consent/assent to collect and use further data

Note: In the United States, the authorization to use and disclose data for research can only be revoked in writing by the subject, or parent or legally-authorized representative of minor subjects.

8.4. Subjects of Childbearing Potential

Female subjects of reproductive potential, and all male subjects must use a medically accepted contraceptive regimen during their participation in the study and for 30 days after the last dose of migalastat. A medically acceptable birth control method is defined as one which results in a low failure rate (ie, < 1% per year) when used consistently and correctly.

A female subject is considered of reproductive potential if she has functional ovaries, ducts, and uterus with no impairment that would cause sterility. This includes females with oligomenorrhea (even severe), and females who have just begun to menstruate.

A female is considered of non-reproductive potential if she is at least 26 weeks status-post documented surgical sterilization (includes hysterectomy, bilateral oophorectomy, bilateral tubal ligation, or salpingectomy).

The allowed methods of contraception described in the following text are only effective when used consistently, correctly, and, if applicable, in accordance with the product label. The investigator is responsible for ensuring subjects understand how to properly use these methods of contraception.

Medically acceptable methods of contraception for female subjects enrolled in the study include the following:

- total abstinence, which refers to refraining from penile-vaginal intercourse, when this is the female's preferred and usual lifestyle
- hormonal contraception (ie, combination oral contraceptive pills, implant, injection, ring, or patch) for at least 12 weeks before baseline
- intrauterine device that meets the < 1% failure per year rate, as stated in the product label, for at least 12 weeks before baseline
- double-barrier method, defined as condom and occlusive cap (eg, diaphragm or cervical/vault caps) used in combination with spermicide (eg, foam, gel, film, cream, suppository)

Note: The double-barrier method does not satisfy the requirements for an effective method of birth control in all countries and may not be utilized as a contraceptive method by subjects participating at sites in those countries

Medically acceptable methods of contraception for male subjects enrolled in the study include the following:

- total abstinence, which refers to refraining from penile-vaginal intercourse, when this is the male's preferred and usual lifestyle
- surgical sterilization (eg, vasectomy with documentation of azoospermia) prior to the subject's entry into the study

Note: For this definition, "documented" refers to the outcome of the investigator's or designee's medical examination of the subject or review of the subject's medical history for study eligibility, as obtained via a verbal interview with the subject or from the subject's medical records.

• double-barrier method, defined as condom and occlusive cap (eg, diaphragm or cervical/vault caps) used in combination with spermicide (eg, foam, gel, film, cream, suppository)

Note: The double-barrier method does not satisfy the requirements for an effective method of birth control in all countries and may not be utilized as a contraceptive method by subjects participating at sites in those countries.

Any pregnancy (in a female subject or the female partner of a male subject) occurring during the study must be reported as described in Section 10.5.1.

In the event of pregnancy in a female subject, migalastat must be discontinued immediately upon becoming aware of the pregnancy. Female subjects or a female partner of a male subject who becomes pregnant during the study must be monitored by the investigator until the outcome of the pregnancy is known. Both the detection and the outcome of the pregnancy must be reported to Amicus.

Periodic abstinence (eg, calendar, ovulation, symptom-thermal, post-ovulation methods) and withdrawal are not acceptable methods of contraception.

9. STUDY ASSESSMENTS AND PROCEDURES

The schedule of study assessments and procedures is presented in Table 2. Total blood volume to be drawn per subject is presented in Table 3.

All study assessments should be conducted by the investigator, and/or a suitably qualified designee. Information will be recorded in the source documents and, where appropriate, the eCRF.

All assessments that occur during the study, where applicable and to the extent possible, should be completed during the designated visit, preferably in the order specified below. Once established, every effort should be made to maintain the order of procedures at each study visit throughout the study.

Assessments	Baseline ^a	line ^a Treatment Period						EOT/ ET	Follow-up		
Visit Interval	Day 1	Month 3 (TC)	Month 6	Month 9 (TC)	Month 12	Month 15 (TC)	Month 18	Month 21 (TC)	Month 24		30-Day Safety
Visit Window (days)		±6	±6	±6	±6	±6	±6	±6	±6	±6	+6
Informed consent/assent	Х										
Inclusion/exclusion criteria	Х										
Medical history	Х										
Concomitant medications	Х	Х	X	X	Х	Х	X	X	X	Х	
Dosing diary ^b	Х	\rightarrow	\rightarrow	\rightarrow	X	\rightarrow	\rightarrow	\rightarrow	X		
FPHPQ questionnaire	Х		X		Х		X		X	Х	
PedsQL	Х		X		Х		X		X	Х	
Complete physical examination	X		Х		Х		Х		X	X	
Adverse events		Х	X	X	X	Х	X	X	X	X	X
Vital signs (BP, HR, RR, Temp)	X		X		Х		X		X	X	
Body weight	Х		X		X		X		X	X	
Height	Х		X		X		X		X	X	
Tanner Staging	Х		X		Х		X		X	Х	
12-lead ECG	Х		X		X		X		X	X	
Chemistry (including eGFR using Schwartz formula)	X		Х		Х		Х		X	Х	
Hematology	Х		X		Х		X		X	Х	

Table 2:Schedule of Assessments

19 August 2021 Confidential

Assessments	Baseline ^a	Treatment Period					EOT/ ET	Follow-up			
Visit Interval	Day 1	Month 3 (TC)	Month 6	Month 9 (TC)	Month 12	Month 15 (TC)	Month 18	Month 21 (TC)	Month 24		30-Day Safety
Visit Window (days)		±6	±6	±6	±6	±6	±6	±6	±6	±6	+6
Plasma lyso-Gb ₃ , analogs, and exploratory PD biomarkers	X		Х		X		Х		Х	Х	
Urinalysis (urine protein, albumin and microalbumin levels)	X		Х		X		Х		Х	Х	
Urine pregnancy test or date of LMP (as applicable) ^c	X	Х	Х	X	X	Х	Х	Х	Х	Х	Х
Echocardiogram (LVMi and additional parameters)	X				X				Х	Х	
Study treatment supply/resupply/ return	X		Х		Х		Х		Х	X ^d	

Table 2:Schedule of Assessments (Continued)

Abbreviations: BP = blood pressure; ECG = electrocardiogram; eGFR = estimated glomerular filtration rate; EOT = end of treatment; ET = early termination; FPHPQ = Fabry-Specific Pediatric Health and Pain Questionnaire; HR = heart rate; LMP = last menstrual period; LVMi = left ventricular mass index; lyso-Gb₃ = globotriaosylsphingosine; PD = pharmacodynamic; PedsQL = Pediatric Quality of Life Inventory; RR = respiration rate; TC = telephone call; Temp = body temperature

Note: Following Month 24, visits will continue every 6 months with interim telephone contacts at 3-month intervals. The assessment schedule will repeat starting from Month 3.

Note: For the purposes of this study, a month is considered to be 30 days.

^a End of study assessments from Study AT1001-020 will be used as baseline assessments for Study AT1001-036.

^b A dosing diary will be completed throughout the treatment period.

^c Female subjects only; urine pregnancy tests will be conducted at each site visit. For menstruating females, date of LMP will be elicited during telephone contacts.

^d Return of study drug only.

Assessments	Baseline ^a	Month 6	Month 12	Total
Chemistry	4	4	4	12
Hematology	2	2	2	6
Plasma lyso-Gb ₃ and PD biomarkers	4	4	4	12
			Total:	30 mL

Table 3: Total Blood Volume to be Collected (as Scheduled) per Subject per Year

Abbreviations: lyso-Gb₃ = globotriaosylsphingosine; PD = pharmacodynamic

Note: Total collection volume does not take into account additional blood samples drawn during potential unscheduled visits.

^a End of study laboratory assessments for Study AT1001-020 will be used as Visit 1 assessments for Study AT1001-036. The blood volume from baseline assessments should not be counted for subsequent years.

9.1. Description of Study Visits

9.1.1. Unscheduled Visits

Unscheduled visits for medical reasons such as evaluation of AEs and/or repeat laboratory tests can be performed at any time at the investigator's discretion. The date and reason for the visit, in addition to all information collected during the visit, should be captured in source documents and on the appropriate eCRFs.

9.1.2. Baseline Visit

Baseline assessments will be performed pre-dose on Day 1. Since subjects will be transitioning from a previous migalastat study, the final visit of that study will be utilized to satisfy any duplicate Visit 1 (baseline) procedures required for the current study. The desired intent is for treatment with migalastat to continue without a break. However, any subject who did not receive migalastat for more than 30 days will be required to repeat all Visit 1 procedures.

All inclusion/exclusion criteria must be reviewed and verified at this visit to ensure that there have been no changes to a subject's health that would affect that subject's eligibility to participate in the study.

9.1.3. Treatment Period Visits/Telephone Contacts

Periodic visits are scheduled every 6 months during the treatment period (ie, at Months 6, 12, etc). Telephone contacts are scheduled at 3-month intervals in between site visits (ie, Months 3, 9, 15, 21, etc). A month will be defined as 30 days. After the first year on study, visits will continue at 6-month intervals with interim telephone contact at intervening 3-month intervals. Following Month 24, the schedule of assessments as displayed in Table 2 will repeat starting with the Month 3 telephone contact (which will be Month 27).

Telephone contacts will include questions regarding any AEs or pregnancies (ie, including delay in menstrual period for female subjects with regular menses) that may have occurred and any changes in concomitant medications.

9.1.4. Early Termination Visit

Subjects who are withdrawn from the study should complete early termination procedures as soon as possible. If early termination coincides with a scheduled visit, all procedures outlined for the early termination visit should be performed.

9.1.5. **30-day Safety Follow-up Visit**

All subjects, including subjects who discontinue study drug or withdraw from the study, should complete a 30-day safety follow-up visit, to be scheduled at least 30 days after the last dose of study drug. This visit may be accomplished by a telephone contact, similar to the scheduled telephone contact. In these instances, in lieu of a urine pregnancy test for female subjects, subjects will be questioned about any pregnancies (ie, including delay in menstrual period for female subjects with regular menses) that may have occurred.

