3.6. Study Procedures and Flowchart

Table 1 details the schedule of assessments:

Table 1. Schedule of Assessments

Assessments	Baseline ^a		Treatment Period					EOT/ ET	Follow- up		
Visit Interval	Day 1	Month 3 (TC)	Month 6	Month 9 (TC)	Month 12	Month 15 (TC)	Month 18	Month 21 (TC)	Month 24		30-Day Safety
Visit Window (days)	—	±6	±6	±6	±6	±6	±6	±6	±6	±6	±6
Informed consent/assent	х										
Inclusion/exclusion criteria	х										
Medical history	х										
Concomitant medications	х	Х	х	х	х	Х	Х	х	х	х	
Dosing diary ^b	х	\rightarrow	\rightarrow	\rightarrow	\rightarrow	\rightarrow	\rightarrow	\rightarrow	х		
FPHPQ questionnaire	х		х		Х		х		х	х	
PedsQL	х		х		Х		х		х	х	
Complete physical examination	х		х		Х		Х		Х	х	
Adverse events		Х	х	х	Х	х	Х	х	х	х	х
Vital signs (BP, HR, RR, Temp)	х		х		Х		Х		х	х	
Body weight	х		х		Х		х		х	х	
Height	Х		х		Х		Х		х	х	
Tanner Staging	х		х		Х		Х		х	х	
12-lead ECG	х		х		Х		Х		х	х	

Assessments	Baseline ^a		Treatment Period							EOT/ ET	Follow-up
Visit Interval	Day 1	Month 3 (TC)	Month 6	Month 9 (TC)	Month 12	Month 15 (TC)	Month 18	Month 21 (TC)	Month 24		30-Day Safety
Visit Window (days)	—	±6	±6	±6	±6	±6	±6	±6	±6	±6	+6
Chemistry (including eGFR using Schwartz formula)	х		х		Х		Х		Х	Х	
Hematology	х		х		х		х		х	х	
Plasma lyso-Gb ₃ , analogs, and exploratory PD biomarkers	Х		Х		х		х		х	Х	
Urinalysis (urine protein, albumin and microalbumin levels)	х		х		х		х		х	Х	
Urine pregnancy test or date of LMP (as applicable)°	х	х	Х	Х	Х	х	Х	х	Х	Х	X
Echocardiogram (LVMi and additional parameters)	х				Х				Х	Х	
Study treatment supply/resupply/ return	х		х		х		х		Х	Xd	

Table 1. Schedule of Assessments (Continued)

Abbreviations: BP = blood pressure; ECG = electrocardiogram; eGFR = estimated glomerular filtration rate; EOT = end of treatment; ET = early termination; FPHPQ = Fabry-Specific Pediatric Health and Pain Questionnaire; HR = heart rate; LMP = last menstrual period; LVMi = left ventricular mass index; lyso-Gb₃ = Globotriaosylsphingosine; PD = pharmacodynamic; PedsQL = Pediatric Quality of Life Inventory; RR = respiration rate; TC = telephone call; Temp = body temperature

Note: Following Month 24, visits will continue every 6 months with interim telephone contacts at 3-month intervals. The assessment schedule will repeat starting from Month 3. Note: For the purposes of this study, a month is considered to be 30 days.

^a End of study assessments from Study AT1001-020 will be used as baseline assessments for Study AT1001-036.

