6.4. Concomitant Medications

Medications will be classified as prior (started prior to the first dose of study treatment in the 036 study) and concomitant (continued past or started on or after the first dose of study treatment in the 036 study). Medications starting after the last dose of study drug will not be considered as concomitant but will be flagged as post medications on the listing. All concomitant medications will be summarized.

All prior and concomitant medications will be classified using the ATC classification coded terms and preferred drug names from the WHO-DD.

Summaries of prior and concomitant medications will be presented separately in tabular form using the level 4 ATC term as an upper classification level and the preferred drug name as a lower classification level. All medications will be summarized and sorted alphabetically by level 4 ATC term and preferred drug name within a given level 4 ATC term. The summary will consist of the frequency and percentage of subjects in the enrolled population who used the medication at least once.

For each subject, the medication will be counted only once within a level 4 ATC term and only once under a given preferred drug name. A subject may appear more than once if he/she has more than one concomitant medication coded under different ATC terms or preferred drug names; however, the subject will be counted only once in the overall category.

A by-subject listing with coded terms will also be provided along with calculated study day.

7. Efficacy

Observed values and changes from baseline for each efficacy endpoint in Section 3.2.1 will be summarized by subgroup, ie, sex (male, female), ERT status (ERT naïve, ERT experienced), with descriptive statistics at each scheduled time point based on the enrolled population. Mean plots including standard error bars at each visit for the numerical observed values and changes from baseline of the indicated laboratory assessments, ECHO results and subject questionnaires will be provided by sex (male, female), ERT status (ERT naïve, ERT experienced), and overall, if feasible.

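### Both schedules leave medications blank at the 30-day safety follow-up while collecting AEs there, so AEs after the last study dose cannot be reliably split by migalastat status

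*Protocol*

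**What the plan says.** **Schedules.** In protocol Table 2 the row "Concomitant medications" is marked from baseline to EOT/ET and is empty at the 30-day follow-up. The row "Adverse events" is marked there. SAP 3.6 ("Table 1 details the schedule of assessments") shows the same pattern.

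**Follow-up contact.** Protocol 9.1.5 applies to all subjects, including those who stop study drug, and allows a call: "This visit may be accomplished by a telephone contact, similar to the scheduled telephone contact". Protocol 9.1.3 says scheduled calls cover AEs or pregnancies "that may have occurred and any changes in concomitant medications".

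**Medication recording.** Protocol 7.4 states that "any medication taken at any time throughout the study must be recorded in the eCRFs", with dates of administration. SAP 6.4 adds: "Medications starting after the last dose of study drug will not be considered as concomitant but will be flagged as post medications". Protocol 11.4.4.8 plans the same flag.

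**Routes out of the study.** Under protocol 7.1, subjects who can obtain reimbursed product "will be switched to Galafold, if continued treatment with migalastat is desired". Early-access or other programs are also mentioned. Protocol 8.3.1 lists eligibility for reimbursed product as a reason for withdrawal, and 7.5 makes use of enzyme replacement a cause of withdrawal.

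**Analysis.** Protocol 10.1.1 collects AEs through the follow-up visit. SAP 9.2 defines a TEAE by onset on or after the first 036 dose, with no end date, and divides total events by patient-years of exposure. SAP 9.1 ends exposure at the last dose.

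**The concern.** The 30 days after the last study dose need not be drug-free. A subject who transfers to commercial migalastat continues the same active substance, another may start enzyme replacement, and a third may take nothing. An AE in that window means something different in each case: an event on continued migalastat, an event on a new therapy, or an event off treatment.

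The schedule has sites ask about AEs at this contact without marking the item that would tell these cases apart. The SAP then pools the events as TEAEs. Long-term safety is the primary objective, so both the description of late events and the exposure-adjusted rate are affected.

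**Working it through.** **1. Count the marks (same result in protocol Table 2 and SAP Table 1).**

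| Row | Baseline | Months 3 to 24 | EOT/ET | 30-day follow-up | Total |
|---|---|---|---|---|---|
| Medications | 1 | 8 | 1 | 0 | 10 |
| AEs | 0 | 8 | 1 | 1 | 10 |

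The last scheduled medication enquiry is EOT/ET. The last AE enquiry is the follow-up.

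**2. Compare the tables with the text.**

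- *Follow-up by telephone:* 9.1.5 read with 9.1.3 implies that the medication question is asked. The tables say it is not scheduled.
- *Follow-up as a site visit:* the telephone wording does not apply. Only the general rule in 7.4 supports collection, while protocol 9.2 has assessments follow Table 2.
- *Analysis:* protocol 11.4.4.8 and SAP 6.4 expect medications started after the last dose to be in the data, yet the only contact scheduled after EOT/ET does not list them.

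**3. Look for another source of migalastat status.** Protocol 8.3.2 requires the reason for and date of withdrawal in the eCRF. That identifies some likely switchers. However, eligibility for reimbursed product is not a start date, and the listed reasons do not identify transfer to an early-access program or treatment after the sponsor ends the study. No section explicitly requests the start date of commercial migalastat.

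**4. Check the event rate.** The plan gives no figure here, so this is an illustration. Let T be days of exposure and F days of follow-up, and assume a constant AE rate λ throughout.

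- Events counted: λ(T + F)
- Denominator used: T
- Reported rate: λ(T + F)/T, an overstatement of F/T

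F = 30 to 36 days comes from the 30-day follow-up and its +6-day window in protocol Table 2. T uses the protocol's 30-day month. The exposure lengths are assumed, because the documents say only that duration will vary.

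| Exposure | T (days) | 30/T | 36/T |
|---|---|---|---|
| 6 months | 180 | 16.7% | 20.0% |
| 12 months | 360 | 8.3% | 10.0% |
| 24 months | 720 | 4.2% | 5.0% |

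If the AE rate in follow-up is k times the on-study rate, each entry is multiplied by k.

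**The case against.** A reader might infer that on-drug and off-drug events cannot be separated at all, or that medications started after the last dose are largely never captured. The documents do not support either reading. A telephone follow-up carries over the medication question, and the only adaptation 9.1.5 makes is for pregnancy testing. Protocol 7.4 requires medications with dates, and 10.4.2 brings medication information from SAE reports into the eCRF. Withdrawal reason and date are recorded, SAP 6.1 tabulates and lists the reasons, and SAP 9.1 and 9.2 list exposure and all AEs. Events after the last dose can therefore be found by date and set against the withdrawal reason. The investigator also judges causality on all available information (protocol 10.2). These arguments stand, and they reduce the problem from certain loss to capture that is not assured.

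It can also be said that the study is small in ambition: uncontrolled, descriptive, with no sample size calculation. A split display would then be a preference. That has some force for the display taken alone. It does not answer the contradiction between tables and text, or the mismatch between numerator and denominator. Non-serious AEs have no equivalent of the SAE route for medication data.

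Finally, one could compute 30/(360 + 30) = 7.7% for a subject with 12 months on study who switches at once and read it as a bias. It is only a share of calendar time. It is not a share of AEs and does not measure an error in any result.

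**Conclusion.** The concern holds as an internal inconsistency with a consequence for the safety analysis. A site that follows either schedule as printed can complete the follow-up without recording a switch to commercial migalastat or a start of enzyme replacement. Separation of post-dose AEs by migalastat status is then unreliable, though not impossible.

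The number of events affected cannot be given, because the documents state neither the share of subjects who switch nor an AE rate. The effect on the event rate is 4.2% to 20.0% over the assumed exposures of 6 to 24 months. It rests on a constant AE rate and a completed follow-up of 30 to 36 days. This part arises from the SAP's definitions and would remain even if every medication were recorded. It should be corrected, but it does not threaten the study.

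**What to change.** 1. Mark concomitant medications at the 30-day follow-up in protocol Table 2 and SAP Table 1, so that both agree with protocol 7.4, 9.1.3 and 9.1.5 whether the contact is a call or a visit.
2. At that contact, record any commercial migalastat, enzyme replacement or other Fabry therapy started since the last study dose, with its start date.
3. In SAP 9.2, show TEAEs with onset after the last study dose separately, by whether the subject was still taking migalastat.
4. In the same section, either leave those events out of the exposure-adjusted rate or add the matching follow-up person-time to the denominator, and say which.

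The cost is one mark in each table, one question at a contact that already takes place, one split display and a sentence on the rate. No dosing or clinical rule changes.
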